6.4. Concomitant Medications, Supportive Care, Excluded Therapies and Restrictions

Medications or vaccinations specifically prohibited in the exclusion criteria are not allowed during the ongoing trial. If there is a clinical indication for any medication or vaccination specifically prohibited during the trial, discontinuation from trial therapy or vaccination may be required. The final decision on any supportive therapy or vaccination rests with the investigator and/or the subject's primary physician.

6.4.1. Acceptable Concomitant Medications

All treatments that the investigator considers necessary for a subject's welfare may be administered at the discretion of the investigator in keeping with the community standards of medical care. All concomitant medication received within 28 days before the first dose of trial treatment and 30 days after the last dose of trial treatment, will be recorded on the case report form (CRF) including all prescription, over-the-counter (OTC), herbal supplements,

and IV medications and fluids. If changes occur during the trial period, documentation of drug dosage, frequency, route, and date may also be included on the CRF. Patients may receive supportive blood products or antibiotics when appropriate. Patients requiring other supportive or adjunctive therapies, including but not limited to percutaneous drainage or biliary or genitourinary stent placement, may be considered on an individual patient basis to be permitted to hold investigational therapy for up to 42 days. Palliative radiation therapy is permitted for irradiating small areas of painful metastases (bony, or otherwise) or bleeding from a solitary site that cannot be managed adequately using systemic or local analgesics, as long as the treating clinician feels the patient is otherwise clinically benefitting and would more likely than not continue to garner benefit at the conclusion of this localized therapy.

Concomitant medications administered after 30 days after the last dose of trial treatment should be recorded for SAEs and ECIs as defined in Section 9.0.

6.4.2. Prohibited Concomitant Medications

Subjects are prohibited from receiving the following therapies during the Screening and Treatment Phase of this trial:

- Antineoplastic systemic chemotherapy or biological therapy
- Immunotherapy not specified in this protocol
- Chemotherapy not specified in this protocol
- Investigational agents other than pembrolizumab
- Radiation therapy

Note: Radiation therapy to a symptomatic solitary lesion or to the brain may be allowed at the investigator's discretion.

- Live vaccines within 30 days prior to the first dose of trial treatment and while participating in the trial. Examples of live vaccines include, but are not limited to, the following: measles, mumps, rubella, varicella/zoster, yellow fever, rabies, BCG, and typhoid vaccine.
- Systemic glucocorticoids for any purpose other than to modulate symptoms from an event of clinical interest of suspected immunologic etiology. The use of physiologic doses of corticosteroids may be approved after consultation with the Sponsor.

Subjects who, in the assessment by the investigator, require the use of any of the aforementioned treatments for clinical management should be removed from the trial. Subjects may receive other medications that the investigator deems to be medically necessary.

The Exclusion Criteria describes other medications which are prohibited in this trial.

There are no prohibited therapies during the Post-Treatment Follow-up Phase

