6.6. Participant Withdrawal/Discontinuation Criteria

Participants may withdraw consent at any time for any reason or be dropped from the trial at the discretion of the investigator should any untoward effect occur. In addition, a participant may be withdrawn by the investigator if enrollment into the trial is inappropriate, the trial plan is violated, or for administrative and/or other safety reasons. Specific details regarding discontinuation or withdrawal are provided in section 8.4 – Other Procedures.

A participant must be discontinued from the trial for any of the following reasons:

- The subject or legal representative (such as a parent or legal guardian) withdraws consent.
- Disease progression (for definition see Section12)
- Unacceptable adverse experiences as described in Section 7.0
- Intercurrent illness that prevents further administration of treatment
- Investigator's decision to withdraw the subject
- The participant has a confirmed positive serum pregnancy test
- Noncompliance with trial treatment or procedure requirements
- The subject is lost to follow-up
- Completed 35 cycles of treatment with pembrolizumab

Note: Subjects who stop pembrolizumab after 35 cycles may be eligible for up to 18 cycles of additional study treatment if they progress after stopping study treatment provided they meet the requirements detailed in Section8.5.4.

• Administrative reasons

The End of Treatment and Follow-up visit procedures are listed in Section 10 (Study calendar) and Section 8.5 (Visit Requirements). After the end of treatment, each subject will be followed for 120 days for adverse event monitoring (events of clinical interest will be collected for 120 days after the end of treatment). Subjects who discontinue for reasons other than progressive disease will have post-treatment follow-up for disease status until disease progression, initiating a non-study cancer treatment, withdrawing consent or becoming lost to follow-up. After documented disease progression each subject will be followed by telephone for overall survival until death, withdrawal of consent, or the end of the study, whichever occurs first.

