8.1.6. Prior Treatment Details

The investigator or qualified designee will review all prior cancer treatments including systemic treatments, radiation and surgeries.

Subsequent Anti-Cancer Therapy Status

The investigator or qualified designee will review all new anti-neoplastic therapy initiated after the last dose of trial treatment. If a subject initiates a new anti-cancer therapy within 30 days after the last dose of trial treatment, the 30 day Safety Follow-up visit must occur before the first dose of the new therapy. Once new anti-cancer therapy has been initiated the subject will move into survival follow-up.

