8.5.3. Post-Treatment Visits

Safety Follow-Up Visit

The mandatory Safety Follow-Up Visit should be conducted approximately 30 days after the last dose of trial treatment or before the initiation of a new anti-cancer treatment, whichever comes first. All AEs that occur prior to the 120 day Safety Follow-Up Visit should be recorded. Subjects with an AE of Grade > 1 will be followed until the resolution of the AE to Grade 0-1 or until the beginning of a new anti-neoplastic therapy, whichever occurs first. SAEs that occur within 120 days of the end of treatment or before initiation of a new anti-cancer treatment should also be followed and recorded. Subjects who are eligible for retreatment with pembrolizumab (as described in Section 8.5.4) may have up to two safety follow-up visits, one after the Treatment Period and one after the Second Course Phase.

Follow-up Visits

Subjects who discontinue trial treatment for a reason other than disease progression will move into the Follow-Up Phase and should be assessed every 9 weeks $(63 \pm 7 \text{ days})$ by radiologic imaging to monitor disease status. After 1 year, the imaging time point will occur every 12 weeks (\pm 7 days). Every effort should be made to collect information regarding disease status until the start of new anti-neoplastic therapy, disease progression, death, end of the study or if the subject begins retreatment with pembrolizumab as detailed in Section 8.5.4. Information regarding post-study anti-neoplastic treatment will be collected if new treatment is initiated.

Survival Follow-up

Once a subject experiences confirmed disease progression or starts a new anti-cancer therapy, the subject moves into the survival follow-up phase and should be contacted by telephone every 12 weeks to assess for survival status until death, withdrawal of consent, or the end of the study, whichever occurs first.

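### Sections 6.4.1 and 6.4.2 differ on whether a benefitting patient who needs palliative radiation to several painful non-brain metastases may stay on pembrolizumab; separately, section 12 has no local rule for target lesions irradiated on study

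*Combined protocol and SAP*

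**What the plan says.** Section 6.4.1 (acceptable concomitant medications) states: "Palliative radiation therapy is permitted for irradiating small areas of painful metastases (bony, or otherwise) or bleeding from a solitary site". The symptom must not be adequately controlled by analgesics, and the permission applies "as long as the treating clinician feels the patient is otherwise clinically benefitting" and is likely to go on benefitting.

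Section 6.4.2 (prohibited concomitant medications) includes radiation in its list for the screening and treatment phase, with this note: "Radiation therapy to a symptomatic solitary lesion or to the brain may be allowed at the investigator's discretion". It then says that subjects who, in the investigator's assessment, "require the use of any of the aforementioned treatments for clinical management should be removed from the trial".

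The parent section, 6.4, says that stopping trial therapy may be required if a prohibited medication is clinically indicated. It adds: "The final decision on any supportive therapy or vaccination rests with the investigator" and/or the subject's primary physician. Neither 6.4.1 nor 6.4.2 refers to the other.

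On irradiated lesions, section 12.2 says only that a lesion in a previously irradiated field may or may not be measurable. Section 12.4 defines PR as at least a 30% fall in the target-lesion sum from baseline and makes no provision for radiation given on study.

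**The concern.** Every patient has metastatic disease, and 6.4.1 itself foresees painful metastases. An investigator with a benefitting patient who has two painful non-brain lesions can irradiate and continue under 6.4.1. Under 6.4.2 read literally, the same patient should come off the trial. Two sites could act differently and each could cite the protocol. The direct consequence concerns treatment: a patient judged to be benefitting keeps or loses the drug according to which section is read.

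A separate omission sits beside this. Both sections allow some radiation during treatment, and the primary endpoint is an investigator-determined response rate in a single arm. If a target lesion is irradiated, 12.4 applied as written counts the resulting shrinkage towards PR. Confirmation at four weeks or more does not separate radiation effect from drug effect.

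**Working it through.** **Comparing the two sections.** I read a solitary lesion in 6.4.2 as a single symptomatic lesion, not as the patient's only lesion.

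| Situation | 6.4.1 | 6.4.2 | Result |
|---|---|---|---|
| One painful lesion, patient benefitting | Permitted | May be allowed | Agree |
| Bleeding from one site, patient benefitting | Permitted | May be allowed | Agree |
| Brain | No specific provision | May be allowed | 6.4.2 is wider |
| One symptomatic lesion, patient not otherwise benefitting | Condition not met | May be allowed | 6.4.2 is wider |
| More than one painful non-brain metastasis, patient benefitting | Permitted | Prohibited; should be removed | Conflict |

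Only the last row gives opposed instructions. The reason is that 6.4.1 attaches the solitary limit to bleeding, while 6.4.2 attaches it to every non-brain field.

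**The design, for context.** Section 13.1 gives n = 21, a null rate of 0.05, an alternative of 0.20, and rejection at 3 or more responses.

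P(X ≥ 3) = 1 − Σ(i = 0 to 2) C(21, i) p^i (1 − p)^(21 − i)

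- p = 0.05: 0.0849 (stated 8.5%).
- p = 0.20: 0.8213 (stated 82.1%).

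Both reproduce, and neither depends on the radiation wording.

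**What an irradiated target lesion could do.** This is a bound, not an estimate. Assume k target lesions of equal diameter (12.2 allows at most 5, and at most 2 per organ), with each irradiated lesion disappearing and the others unchanged. The fall in the sum is m/k for m irradiated lesions, against the 30% PR threshold in 12.4.

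| k | One irradiated (1/k) | Two irradiated (2/k) |
|---|---|---|
| 1 | 100% | – |
| 2 | 50% | 100% |
| 3 | 33.3% | 66.7% |
| 4 | 25% | 50% |
| 5 | 20% | 40% |

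One irradiated lesion passes 30% with 1 to 3 targets but not with 4 or 5. Two pass it even at the maximum of 5. Section 12.2 classes bone lesions as non-measurable, so radiation to bone cannot act through this route; the bound applies to non-bone target lesions only.

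One miscredited response changes the conclusion only at the cutoff: 2/21 = 9.5% does not reject, and 3/21 = 14.3% does.

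**The case against.** The best reply on the conflict is that it rests on loose drafting. The plural in 6.4.1 may be generic. The sentence also runs its pain and bleeding limbs together: its analgesic clause follows the bleeding limb, though analgesics treat pain. The solitary limit might therefore have been meant for both. The note in 6.4.2 does not say that its exceptions are the only ones, removal is worded as something that should happen, and 6.4 gives clinicians the last word. All of this softens the conflict. It does not remove it, because nothing says which section prevails, and a benign reading has to be chosen by the site.

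A reader might infer that patients removed under 6.4.2 lose their scans and so bias ORR or PFS. The documents do not support that. Section 8.5.3 says: "Subjects who discontinue trial treatment for a reason other than disease progression will move into the Follow-Up Phase". Section 6.6 says that those who stop for reasons other than progression "will have post-treatment follow-up for disease status until disease progression, initiating a non-study cancer treatment", among other end points, and the calendar footnote also continues imaging. Imaging would end only if palliative radiation were read as new anti-cancer therapy. Section 8.1.6 speaks of therapy begun after the last trial dose and requires that the 30-day safety visit "must occur before the first dose of the new therapy", which fits drugs better than a palliative field.

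A reader might also take the lesion arithmetic as the size of the conflict. It is not. That issue arises even where the two sections agree, and it remains whichever radiation rule is kept. It is also fair to say that section 12 adopts RECIST 1.1, whose publication is not part of these documents; what is established is only that the protocol has no text of its own on the point.

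**Conclusion.** The inconsistency is real but narrow and minor. It concerns a benefitting patient who needs palliative radiation to more than one painful non-brain metastasis, with 6.4.2 read literally. It affects whether that patient continues pembrolizumab. It has no demonstrated effect on response, PFS, sample size, alpha or power. Its frequency is unknown because the documents give no rate of on-study radiation.

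The missing target-lesion rule is a separate omission, worth closing because the trial is decided at 3 responses in 21. The calculation shows that irradiating a non-bone target lesion could reach the PR threshold under the stated assumptions. It does not show that this is likely, and no effect on ORR can be estimated.

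**What to change.** 1. State one radiation rule in both 6.4.1 and 6.4.2. It would combine small painful areas or solitary-site bleeding in a benefitting patient (from 6.4.1) with a symptomatic solitary lesion or the brain at the investigator's discretion (from 6.4.2), and say that pembrolizumab continues. If the solitary limit in 6.4.2 was deliberate, apply that limit in both sections instead.
2. In 6.4.2, replace removal from the trial with discontinuation of trial treatment, with follow-up per 6.6 and 8.5.3.
3. Separately, add to 12.4 that a non-bone target lesion irradiated on study is carried at no less than its last pre-radiation diameter when judging CR or PR; that growth or new lesions still count as PD; and that the patient stays in the response denominator and is not replaced. The last clause is needed because 13.1 replaces patients who are not evaluable for response.

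The cost is wording only, with no new procedures and no change to sample size, alpha or power. The downside is that a true responder whose main target lesion is irradiated may not be counted: if a patient's only target lesion is irradiated before it has shrunk by 30%, that patient can no longer reach PR.

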6.4.3. Rescue Medications & Supportive Care

Subjects should receive appropriate supportive care measures as deemed necessary by the treating investigator. Suggested supportive care measures for the management of adverse events with potential immunologic etiology are outlined below and in greater detail in appendix (section 17.3). Where appropriate, these guidelines include the use of oral or intravenous treatment with corticosteroids as well as additional anti-inflammatory agents if symptoms do not improve with administration of corticosteroids. Note that several courses of steroid tapering may be necessary as symptoms may worsen when the steroid dose is decreased. For each disorder, attempts should be made to rule out other causes such as metastatic disease or bacterial or viral infection, which might require additional supportive care. The treatment guidelines are intended to be applied when the investigator determines the events to be related to Pembrolizumab.

Note: if after the evaluation the event is determined not to be related, the investigator may follow the AE reporting guidance but does not need to follow the treatment guidance (as outlined in appendix 17.3). Refer to section 7.0 for dose modification.

It may be necessary to perform conditional procedures such as bronchoscopy, endoscopy, or skin photography as part of evaluation of the event. Suggested conditional procedures, as appropriate, can be found in the ECI guidance document.

Pneumonitis:

- For **Grade 2 events**, treat with systemic corticosteroids. When symptoms improve to Grade 1 or less, steroid taper should be started and continued over no less than 4 weeks.
- For Grade 3-4 events, immediately treat with intravenous steroids. Administer additional anti-inflammatory measures, as needed.
- Add prophylactic antibiotics for opportunistic infections in the case of prolonged steroid administration.

Diarrhea/Colitis:

Subjects should be carefully monitored for signs and symptoms of enterocolitis (such as diarrhea, abdominal pain, blood or mucus in stool, with or without fever) and of bowel perforation (such as peritoneal signs and ileus).

- All subjects who experience diarrhea/colitis should be advised to drink liberal quantities of clear fluids. If sufficient oral fluid intake is not feasible, fluid and electrolytes should be substituted via IV infusion. For Grade 2 or higher diarrhea, consider GI consultation and endoscopy to confirm or rule out colitis.
- For Grade 2 diarrhea/colitis that persists greater than 3 days, administer oral corticosteroids.
- For **Grade 3 or 4 diarrhea/colitis** that persists > 1 week, treat with intravenous steroids followed by high dose oral steroids.
- When symptoms improve to Grade 1 or less, steroid taper should be started and continued over no less than 4 weeks.

Type 1 diabetes mellitus (if new onset, including diabetic ketoacidosis [DKA]) or \geq Grade 3 Hyperglycemia, if associated with ketosis (ketonuria) or metabolic acidosis (DKA)

- Insulin replacement therapy is recommended for Type I diabetes mellitus and for Grade 3-4 hyperglycemia associated with metabolic acidosis or ketonuria.
- Evaluate patients with serum glucose and a metabolic panel, urine ketones, glycosylated hemoglobin, and C-peptide.

Hypophysitis:

- For **Grade 2** events, treat with corticosteroids. When symptoms improve to Grade 1 or less, steroid taper should be started and continued over no less than 4 weeks. Replacement of appropriate hormones may be required as the steroid dose is tapered.
- For **Grade 3-4** events, treat with an initial dose of IV corticosteroids followed by oral corticosteroids. When symptoms improve to Grade 1 or less, steroid taper should be started and continued over no less than 4 weeks. Replacement of appropriate hormones may be required as the steroid dose is tapered.

Hyperthyroidism or Hypothyroidism:

Thyroid disorders can occur at any time during treatment. Monitor patients for changes in thyroid function (at the start of treatment, periodically during treatment, and as indicated based on clinical evaluation) and for clinical signs and symptoms of thyroid disorders.

- Grade 2 hyperthyroidism events (and Grade 3-4 hypothyroidism):
 - \circ In hyperthyroidism, non-selective beta-blockers (e.g. propranolol) are suggested as initial therapy.
 - In hypothyroidism, thyroid hormone replacement therapy, with levothyroxine or liothyroinine, is indicated per standard of care.
- Grade 3-4 hyperthyroidism
 - Treat with an initial dose of IV corticosteroid followed by oral corticosteroids. When symptoms improve to Grade 1 or less, steroid taper should be started and continued over no less than 4 weeks. Replacement of appropriate hormones may be required as the steroid dose is tapered.

Hepatic:

- For **Grade 2** events, monitor liver function tests more frequently until returned to baseline values (consider weekly).
 - o Treat with IV or oral corticosteroids
- For Grade 3-4 events, treat with intravenous corticosteroids for 24 to 48 hours.
- When symptoms improve to Grade 1 or less, a steroid taper should be started and continued over no less than 4 weeks.

Renal Failure or Nephritis:

- For Grade 2 events, treat with corticosteroids.
- For Grade 3-4 events, treat with systemic corticosteroids.
- When symptoms improve to Grade 1 or less, steroid taper should be started and continued over no less than 4 weeks.

Management of Infusion Reactions: Signs and symptoms usually develop during or shortly after drug infusion and generally resolve completely within 24 hours of completion of infusion. Table 2 below shows treatment guidelines for subjects who experience an infusion reaction associated with administration of Pembrolizumab.

NCI CTCAE Grade	Treatment	Premedication at subsequent dosing	
Grade 1 Mild reaction; infusion interruption not indicated; intervention not indicated	Increase monitoring of vital signs as medically indicated until the subject is deemed medically stable in the opinion of the investigator.	None	
Grade 2 Requires infusion interruption but responds promptly to symptomatic treatment (e.g., antihistamines, NSAIDS, narcotics, IV fluids); prophylactic medications indicated for < =24 hrs	Stop Infusion and monitor symptoms. Additional appropriate medical therapy may include but is not limited to: IV fluids Antihistamines NSAIDS Acetaminophen Narcotics Increase monitoring of vital signs as medically indicated until the subject is deemed medically stable in the opinion of the investigator. If symptoms resolve within one hour of stopping drug infusion, the infusion may be restarted at 50% of the original infusion rate (e.g., from 100 mL/hr to 50 mL/hr). Otherwise dosing will be held until symptoms resolve and the subject should be premedicated for the next scheduled dose. Subjects who develop Grade 2 toxicity despite adequate premedication should be permanently discontinued from further trial treatment administration.	Subject may be premedicated 1.5h (± 30 minutes) prior to infusion of Pembrolizumab with: Diphenhydramine 50 mg po (or equivalent dose of antihistamine). Acetaminophen 500-1000 mg po (or equivalent dose of antipyretic).	
Grades 3 or 4 Grade 3: Prolonged (i.e., not rapidly responsive to symptomatic medication and/or brief interruption of infusion); recurrence of symptoms following initial improvement; hospitalization indicated for other clinical sequelae (e.g., renal impairment, pulmonary infiltrates) Grade 4: Life-threatening; pressor or ventilatory support indicated	Stop Infusion. Additional appropriate medical therapy may include but is not limited to: IV fluids Antihistamines NSAIDS Acetaminophen Narcotics Oxygen Pressors Corticosteroids Epinephrine Increase monitoring of vital signs as medically indicated until the subject is deemed medically stable in the opinion of the investigator. Hospitalization may be indicated. Subject is permanently discontinued from further trial treatment administration.	No subsequent dosing	

 Table 2. Infusion Reaction Treatment Guidelines

NCI CTCAE Grade	Treatment	Premedication at subsequent
		dosing

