9.1.4. Severity Rating

The investigator will evaluate the severity of each adverse event. NCI Common Terminology Criteria for Adverse Events (CTCAE v.4.0) or study specific toxicity tables provided in the protocol define severity. If not included in CTCAE v.4.0, severity is expressed in numerical grade using the following definitions:

- 1. Grade 1: Mild-asymptomatic or mild symptoms; clinical or diagnostic observations only; intervention not indicated.
- 2. Grade 2: Moderate-minimal, local or noninvasive intervention indicated; limiting age appropriate instrumental ADL.
- 3. Grade 3: Severe-severe or medically significant but not immediately lifethreatening; hospitalization or prolongation of hospitalization indicated; disabling; limiting self care ADL.
- 4. Grade 4: Life-threatening consequences; urgent intervention indicated.
- 5. Grade 5: Death related to AE

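### Section 6.4.3 prompts steroids later for Grade 3 or 4 diarrhea/colitis (more than 1 week) than for Grade 2 (more than 3 days)

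*Combined protocol and SAP*

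**What the plan says.** Section 6.4.3 sets out supportive care for adverse events with a possible immune cause. Two adjacent bullets under diarrhea/colitis say when to start steroids:

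- Grade 2: "For Grade 2 diarrhea/colitis that persists greater than 3 days, administer oral corticosteroids".
- Grade 3 or 4: steroids for an event "that persists > 1 week, treat with intravenous steroids followed by high dose oral steroids".

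The same block asks sites to watch for enterocolitis and bowel perforation, and to consider GI consultation and endoscopy from Grade 2 upward. The section describes its measures as suggestions. They apply once the investigator judges the event related to pembrolizumab, and other causes such as infection should be looked for. Further detail is said to be in Appendix 17.3, which is supplied as a separate PDF.

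**The concern.** A trigger based on how long an event lasts would be expected to shorten, or disappear, as the grade rises. Here it lengthens. A site that follows the bullets literally is prompted to treat the milder event first and the more severe one later, in a condition where the section itself warns about perforation.

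What is at stake is patient care at the sites. This is not a point about the efficacy analysis.

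**Working it through.** There is no plan figure to reproduce and no formula beyond a subtraction. The check compares the text of 6.4.3 with itself, then looks for anything elsewhere that corrects it.

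**1. The two thresholds.** Grade 2: more than 3 days. Grade 3 or 4: more than 1 week, that is more than 7 days. Difference: 7 − 3 = 4 days, with the longer wait at the higher grade. On day 5 the Grade 2 condition is met (5 > 3) and the Grade 3 or 4 condition is not (5 < 7).

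The text does not say whether persistence is counted from onset or from reaching the grade. The 4 days is therefore the gap between two printed thresholds, not a measured delay in any patient. A patient who had already spent more than 3 days at Grade 2 would have met the Grade 2 trigger. The gap matters most for someone who reaches Grade 3 or 4 quickly.

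**2. Every Grade 3-4 instruction in 6.4.3 that directs steroids.**

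| Event | Instruction | Wait before steroids |
|---|---|---|
| Pneumonitis | "For Grade 3-4 events, immediately treat with intravenous steroids" | None |
| Diarrhea/colitis | "that persists > 1 week, treat with intravenous steroids followed by high dose oral steroids" | More than 1 week |
| Hypophysitis | "events, treat with an initial dose of IV corticosteroids followed by oral corticosteroids" | None |
| Hyperthyroidism | "Treat with an initial dose of IV corticosteroid followed by oral corticosteroids" | None |
| Hepatic | "For Grade 3-4 events, treat with intravenous corticosteroids for 24 to 48 hours" | None (the hours are treatment duration) |
| Renal failure or nephritis | "For Grade 3-4 events, treat with systemic corticosteroids" | None |

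With a wait: 1 of 6. Without: 5 of 6. Infusion reactions are left out because Table 2 lists corticosteroids only among therapies that may be used. Type 1 diabetes/hyperglycemia and hypothyroidism are left out because they are directed to hormone replacement.

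**3. Does another section supply an earlier start?**

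- Table 3 (section 7.1) holds pembrolizumab for Grade 2-3 diarrhea/colitis and stops it permanently at Grade 4. It gives no time for starting steroids.
- Section 6.4.2 permits systemic steroids for suspected immune events but does not prompt them.
- Section 9.1.4 describes Grade 4 as "Life-threatening consequences; urgent intervention indicated". That wording formally covers only terms absent from CTCAE v4.0, so it shows how the protocol thinks of Grade 4 and is not a rule for colitis.

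None of these brings the Grade 3 or 4 trigger forward.

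**The case against.** The strongest objection is that Appendix 17.3 may hold the controlling detail. Section 6.4.3 and section 7.1 both send sites there, and it could not be read. That limits what can be said about the guidance as a whole, but it does not rescue the bullet. If the appendix repeats the wait, both texts need correcting. If it gives an earlier start, the protocol body contradicts it.

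A second objection is that the 1-of-6 count proves little. At Grade 2, diarrhea/colitis is again the only steroid-directed event with a wait: pneumonitis, hypophysitis, hepatic and renal events have none. Diarrhea is a symptom that needs a work-up, so some wait could be deliberate. This is fair, and the count is supporting evidence only. The finding rests on the ordering of the two colitis thresholds, and the need for a work-up does not explain why the sicker patient should wait longer.

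Third, the bullets name different treatments, oral versus intravenous then high-dose oral, so they might be read as a step-up. The text does not say that. Neither steroid bullet covers a Grade 3 or 4 patient before one week. The endoscopy bullet just above explicitly includes higher grades, whereas the Grade 2 steroid bullet does not.

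Fourth, nothing compels delay. The measures are suggested, section 6.4.1 allows any treatment the investigator considers necessary, and drug is held or stopped under Table 3. All of this stands, and it limits the seriousness of the point.

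Finally, earlier steroids have a cost. A taper of at least 4 weeks follows improvement, and Table 3 removes a patient with Grade 2-3 colitis who cannot get down to 10 mg prednisone or equivalent within 12 weeks. The documents give no event frequency or rate of spontaneous resolution with which to weigh this. The cost is real and belongs in the decision, but it is no argument for treating Grade 3 or 4 later than Grade 2.

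**Conclusion.** The concern holds. The written steroid triggers for diarrhea/colitis are inverted by severity, with thresholds 4 days apart in the wrong direction, and this is the only one of the six steroid-directed Grade 3-4 instructions in 6.4.3 with a wait. It should be corrected as a flawed safety instruction.

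The conclusion rests on the protocol text alone and uses no outside guideline. It assumes the bullets are read as written, and it leaves open what Appendix 17.3 says. It does not show that any patient was or would be treated late. How often it would matter cannot be estimated, because event frequency is not given. No effect is claimed on the objective response rate, the 3-of-21 rule, the toxicity stopping rule or Table 3's 6-week limit.

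**What to change.** In the Grade 3 or 4 diarrhea/colitis bullet of 6.4.3, strike the persistence clause, which is everything before the comma in "that persists > 1 week, treat with intravenous steroids followed by high dose oral steroids". The bullet then directs any Grade 3 or 4 event to intravenous and then high-dose oral steroids, in line with the other five event types. Leave the Grade 2 bullet as it is. The existing conditions stay in force: the event is judged related to pembrolizumab, and other causes are looked for. Check Appendix 17.3 and align it if it differs.

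The cost is one phrase in one bullet plus the appendix check, with no change to design, sample size or analysis. The clinical price is that some patients will receive a steroid course, with its taper, for an event that would have settled within a week.
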